7.3. Data Pooling

The data poolability of subjects enrolled in the Valiant Evo US Clinical Trial and subjects enrolled in the Valiant Evo International Clinical Trial is assumed given that both study protocols will be similar with respect to, inclusion/exclusion criteria, clinical treatment, definitions of clinical events, one data monitoring plan, Data

Monitoring Committee (DMC), Clinical Event Committee (CEC), Independent Physician Reviewer (IPR) and core imaging laboratory.

At the data analysis stage, the data poolability will be reviewed for the primary endpoint. Results from Valiant Evo US Clinical Trial and Valiant Evo International Clinical Trial subjects will be presented separately for clinical review as well as tested using a Chi-square test.

A poolability analysis among geographies/investigational sites will be assessed descriptively for the primary endpoints by geographic regions. Small investigational sites (less than 5 subjects) will be grouped with other nearby sites for the by-region analysis.

7.4. Handling of Missing Data and Dropouts

During statistical analysis, imputation of missing data will not be performed except for data related to the onset date of an adverse event or a death. In cases where the onset date of an event or a death is incomplete and unresolvable via data query, the 15th day of the known month or July 1st of the known year will be used.

Sensitivity analysis using tipping point method may be performed, as needed, to assess the impact of missing data for the primary endpoint.

7.5. Adjustments for Multiple Comparisons

One hypothesis test on the primary study endpoint will be performed at the time of PMA submission. Therefore, there is no multiple comparisons/multiplicity issue.

When the post-approval analysis is carried out, no multiplicity adjustment is needed due to the fact that the post-approval analysis is conditioning on the PMA approval.

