Subjects will be followed until the last subject enrolled has completed the 1 year follow-up visit or until PMA approval is obtained in the US (whatever is later), however, Medtronic will work with FDA to determine if longer term follow after PMA approval is required. A post-approval analysis of 1-year Major Device Event (MDE) rate is planned.

6. Determination of Sample Size

One hundred (100) enrolled subjects will ensure 87 evaluable subjects at 30 days. The primary endpoint analysis will be completed upon 87 evaluable subjects reaching the 30 day endpoint. Based on Valor II study results, Valiant Evo is expected to perform similarly and have 6% of MDE combined with access and/or deployment failures at 30 days. The sample size of 87 evaluable subjects will provide 85% statistical power for the study hypothesis. The type I error is controlled at the one-sided 0.025 level.

Table 1: Power Analysis

True rate of MDEs combined with access and/or deployment failures at 30 day with Valiant Evo	6%
Performance Goal	16%
Significance level	0.025
Statistical test	One-sided binomial test
Evaluable sample size	n=87
Enrollment	Minimum of 100 subjects enrolled to ensure 87 evaluable subjects
Statistical power from the 87 evaluable subjects	85%

One hundred (100) enrolled subjects will also ensure 63 evaluable subjects at 1-year on MDE rate for the post-approval analysis. The VALOR II study with the Valiant stent graft system enrolled 160 patients with DTAA and was assessed through 12 months for purposes of PMA (P100040) approval. Through 1-year post-

treatment, the rate of MDEs combined with access and/or deployment failures was 7.1% (11/153) (Medtronic internal data using the Valiant Evo proposed definition). Therefore, for the purpose of post approval analysis, the rate of MDEs combined with access and deployment failures at 1-year with Valiant Evo is estimated to be 7.1% (refer to Table 22 below for power analysis assumptions).

Table 2: Power Analysis for Post-approval Analysis of 1-year Endpoint

Estimated rate of MDEs combined with access and/or deployment failures at 1 year with Valiant Evo	7.1%
Performance Goal (PG) at 1-year	20%
Significance level	0.05
Statistical test	One-sided binomial test
Evaluable sample size	N = 63 at 1 year
Enrollment	IDE cohort will enroll a minimum of 100 subjects and is expected to have a minimum of 63 evaluable subjects at 1-year follow up.

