Statistical power from 63 or more evaluable subjects	92% (overall study power for passing both hypotheses is 81%)

7. Statistical Methods

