7.9. Evaluation of Objectives

Primary Endpoint

The primary objective will be assessed by the composite safety and effectiveness endpoint that is based on the proportion of subjects who experienced:

- (a) Access and/or deployment failures; and/or
- (b) Major device effects (MDE) within 30 days post index procedure

MDEs include the occurrence of any of the following:

- Device-related secondary procedures
- Device-related mortality
- Conversion to open surgery
- Thoracic aortic aneurysm rupture

Detailed definitions of MDEs are defined in Clinical Investigational Plan Appendix L.5.

The primary study endpoint will be tested against a performance goal of 16% at 30 days:

$$H_0: p \geq 16\% \text{ vs. } H_a: p < 16\%,$$

where p denotes the true event rate of primary study endpoint in the target population. If the null hypothesis

(H₀) is rejected at the one-sided 0.025 statistical significance level, it is considered that the performance goal for the primary endpoint has been reached.

The analysis set of all enrolled subjects will be used for the analysis. The primary study endpoint is a dichotomous study outcome; hence, an exact method based on the binomial distribution will be used for the hypothesis testing.

Primary Endpoint Calculation:

A subject will be a failure on the primary endpoint if the subject either failed on access/deployment or had an MDE within 30 days. A subject will be a success on the primary endpoint if the subject is confirmed for access and deployment success as well as free from MDE. The failure rate of the primary endpoint is the percent of failures in all the evaluable subjects for the endpoint, i.e., in total number of failures and successes. Note that a subject who had an MDE within 30 days is one of the subjects in m as defined below. A subject who is free from MDE is one of the subjects in k as defined below.

MDE Rate Calculation:

All MDEs will be adjudicated by the Clinical Event Committee (CEC) per study protocol. MDE rate will be calculated as follows (Table 5):

Table 5: MDE Rate Calculation:

MDE rate = $m/(m + k)$	Within 30 Days	Within 183 Days	Within 365 Days
m = No. of Subjects Who Had MDE(s)	No. of subjects who had at least one MDE with onset day from Day 0 to Day 30, inclusive.	No. of subjects who had at least one MDE with onset day from Day 0 to Day 183, inclusive.	No. of subjects who had at least one MDE with onset day from Day 0 to Day 365, inclusive.

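### SAP 7.5 waives multiplicity adjustment for the 1-year test because it follows PMA approval, but approval is not tied to rejecting the 30-day null and so is not a statistical gate

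*SAP*

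**What the plan says.** The SAP sets out two tests against performance goals.

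- **30 days.** Section 7.9: "The primary study endpoint will be tested against a performance goal of 16% at 30 days". If the null "is rejected at the one-sided 0.025 statistical significance level, it is considered that the performance goal for the primary endpoint has been reached". Section 6 adds "The sample size of 87 evaluable subjects will provide 85% statistical power for the study hypothesis" and, at the end of the same paragraph, "The type I error is controlled at the one-sided 0.025 level".
- **1 year.** Section 6, Table 2 gives a goal of 20%, a one-sided binomial test at 0.05, 63 evaluable subjects and 92% power. The planning assumption is that the "rate of MDEs combined with access and deployment failures at 1-year with Valiant Evo is estimated to be 7.1" per cent. The same table reports that "overall study power for passing both hypotheses is 81" per cent.

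Section 7.5 deals with multiplicity in two paragraphs. The first says that a single test is done at PMA submission, so no issue arises. The second covers the later analysis and gives one reason: "no multiplicity adjustment is needed due to the fact that the post-approval analysis is conditioning on the PMA approval".

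Section 5 says only that a 1-year post-approval analysis is planned. Nothing in the SAP makes approval depend on rejecting the 30-day null, and nothing says what happens to the 1-year test if the 30-day test fails.

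**The concern.** A second test needs no share of alpha when it opens only after the first null has been rejected. That is a fixed sequence, and the protection comes from the rejection itself. Approval is a different event. It is an outside decision that may draw on other evidence, and it is not a function of the 30-day test statistic. Conditioning on it does not give fixed-sequence protection, so the reason given in 7.5 does not support its conclusion.

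As the SAP stands, a missed 30-day goal followed by approval would leave the 1-year hypothesis open to formal testing. The report could then show a goal met at 1 year after a failed primary test, with no pre-stated rule on whether that result is confirmatory. Because Section 6 quotes power for passing both tests, a reader would also expect to find the order of testing and the matching error level. Neither is given.

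**Working it through.** **Inputs, all from SAP Section 6, Tables 1 and 2, and Section 7.9**

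- 30 days: n = 87, goal 16%, assumed rate 6%, one-sided 0.025, exact binomial test.
- 1 year: n = 63, goal 20%, assumed rate 7.1%, one-sided 0.05, binomial test (computed here as exact).

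**Assumptions, not in the documents**

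- Every 30-day event also counts at 1 year (nested events).
- Either all 63 one-year subjects are among the 87, or only 50 are.
- g is the chance of approval after a failed 30-day test, from 0 to 1, taken as the same for every failing result.

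**Step 1. Reproduce the stated powers.** The rejection limit is the largest event count whose probability at the goal does not exceed alpha.

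- 30 days: P(X ≤ 7 | 87, 0.16) = 0.0233 and P(X ≤ 8) = 0.0495, so reject at 7 or fewer. Power = P(X ≤ 7 | 87, 0.06) = 0.849 (stated 85%).
- 1 year: P(Y ≤ 7 | 63, 0.20) = 0.0473 and P(Y ≤ 8) = 0.0937, so reject at 7 or fewer. Power = P(Y ≤ 7 | 63, 0.071) = 0.923 (stated 92%).
- Joint power: 0.831 (63 common), 0.818 (50 common), and 0.849 × 0.923 = 0.784 if independent. The stated 81% lies in this range; its derivation is not given.

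**Step 2. Error under a true gate.** Let A be rejection at 30 days and B rejection at 1 year.

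- 30-day null true: a false claim needs A, so the error is at most 0.0233.
- Only the 1-year null true: the error is P(A and B), at most P(B) = 0.0473.
- Worst case: 0.0473, nominal 0.05.

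**Step 3. Error when approval is the only condition.** With both nulls true, error = P(A) + g × [P(B) − P(A and B)]. With both true rates at their goals (16% and 20%), by exact enumeration:

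| Common subjects | P(A) | P(A and B) | P(B) − P(A and B) | g = 0 | g = 0.5 | g = 1 |
|---|---|---|---|---|---|---|
| 63 | 0.0233 | 0.0124 | 0.0349 | 0.023 | 0.041 | 0.058 |
| 50 | 0.0233 | 0.0082 | 0.0391 | 0.023 | 0.043 | 0.063 |

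The error passes 0.05 only if g exceeds (0.05 − 0.0233)/0.0349 ≈ 0.76, or (0.05 − 0.0233)/0.0391 ≈ 0.68. Treating the two tests as independent would give 0.0233 + 0.0473 × (1 − 0.0233) ≈ 0.070 at g = 1. That is an outer reference only, because the same subjects contribute to both tests.

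If only one of the two nulls is true, the lack of a gate does not raise the worst case. It stays at 0.0233 when only the 30-day null is true and 0.0473 when only the 1-year null is true.

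**Step 4. Away from the goals, still at g = 1.** True rates of 18% and 20% give 0.049 (63 common) to 0.051 (50 common). True rates of 16% and 22% give 0.037 to 0.040.

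**Step 5. How often the unaddressed case could arise.** At the SAP's assumed rates (6% and 7.1%), the chance of missing the 30-day goal yet meeting the 1-year goal is P(B) − P(A and B) = 0.923 − 0.831 = 0.092 (63 common), or 0.923 − 0.818 ≈ 0.106 (50 common), before any approval decision. Neither claim would be false there, but the SAP has no rule for that result.

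**The case against.** The strongest reply has five parts.

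1. **No stated error rate is contradicted.** A reader might infer that the SAP promises 0.025 across both tests and breaks that promise. It does not. The 0.025 statement closes the paragraph on the 30-day hypothesis, and Table 2 openly gives the 1-year test 0.05. The first paragraph of 7.5 is also correct for the single test at submission. This stands in full.
2. **The inflation is conditional.** A reader might infer that the error simply exceeds both nominal levels, or might set 0.058 to 0.063 against the gated 0.023. The higher figures need certain approval after a failed 30-day test, although Section 5 makes the 87-subject data the support for approval. They also need both true rates close to their goals. The like-for-like comparison is with the gated worst case of 0.047. This stands too.
3. **Section 7.9 plans no inference on secondary endpoints, and MDEs within 365 days is one of them.** It also gives no explicit 1-year success rule. This weakens the case for a formal 1-year claim, but Table 2 still specifies a goal, a level, a test and a joint power. The SAP therefore points both ways, which is a further reason to state the rule.
4. **The US protocol might contain the gate.** The SAP names it as the source for clarification, and it is not among the documents. The International protocol (C.3 and H.1) is descriptive with no hypothesis. The finding is therefore confined to the SAP text. A gate elsewhere would still not make the reason in 7.5 correct.
5. **A pre-approval and a post-approval test may serve separate decisions.** Whether they form one error family is partly judgement, and quoting joint power does not commit the sponsor to joint error control. It does make the absence of a stated order and level a gap.

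**Conclusion.** The point holds in limited form. The rationale in 7.5 is not a valid gate, because approval is not tied to rejecting the 30-day null and nothing makes the 1-year result descriptive after a failed 30-day test.

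The effect is small. At the extreme (approval certain after failure, both rates at their goals, nested events), the two-test error is 0.058 to 0.063. That is about 1.1 to 1.5 percentage points above the 0.047 worst case of a properly gated plan. For g below about 0.68 to 0.76 it does not pass 0.05. The primary 30-day conclusion and its 0.025 level are untouched. These figures rest on the assumed range of g, the nesting of events and the two overlap cases. This is a minor correction to the SAP, and it does not bear on the descriptive International protocol.

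**What to change.** Replace the second paragraph of SAP 7.5 with wording such as:

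> The 1-year hypothesis is tested only if the 30-day null was rejected at one-sided 0.025; otherwise the 1-year rate is reported descriptively with its exact interval, whatever the approval status.

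Add that the 30-day test is controlled at one-sided 0.025 and the two-test family at 0.05. In 7.9, note that the 1-year hypothesis of Table 2 is the exception to the rule that secondary endpoints carry no inference.

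The cost is two or three sentences and the loss of a formal 1-year claim after a failed 30-day test. Both alpha levels and the sample size stay as they are.

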7.6. Demographic and Other Baseline Characteristics

Descriptive statistics will be provided for demographic (age, gender, and race) and other baseline characteristic variables such as medical history and baseline thoracic aorta measurements. Note that race will be summarized for subjects enrolled in the US only, since collection of race and ethnicity data may not be allowed outside the US as per local law and regulation.

7.7. Treatment Characteristics

The following acute procedural observations and clinical utility measures will be analyzed using descriptive statistics:

- Mean duration (min) of procedure
- Proportion of subjects who underwent general anesthesia
- Proportion of subjects who underwent percutaneous access
- Proportion of subjects requiring blood transfusions

- Mean number of units of blood transfused, if required
- Mean volume (cc) of estimated blood loss
- Mean length of time (hours) in intensive care unit
- Mean length of time (days) of hospital stay (from the index procedure to hospital discharge)

Study device disposition will be summarized by type and size. Number of study devices used on each subject will be analyzed descriptively.

7.8. Interim Analyses

No interim analysis intended for sample size recalculation is planned prior to the PMA submission.

Data reports will be generated for Data Monitoring Committee (DMC) review during the trial. A design dossier including clinical evaluation of the Valiant Evo Stent Graft System will be created for the CE mark submission. However, there is no plan to modify the Valiant Evo US Clinical Trial based on these reports.

7.9. Evaluation of Objectives

Primary Endpoint

The primary objective will be assessed by the composite safety and effectiveness endpoint that is based on the proportion of subjects who experienced:

- (a) Access and/or deployment failures; and/or
- (b) Major device effects (MDE) within 30 days post index procedure

MDEs include the occurrence of any of the following:

- Device-related secondary procedures
- Device-related mortality
- Conversion to open surgery
- Thoracic aortic aneurysm rupture

Detailed definitions of MDEs are defined in Clinical Investigational Plan Appendix L.5.

The primary study endpoint will be tested against a performance goal of 16% at 30 days:

$$H_0: p \geq 16\% \text{ vs. } H_a: p < 16\%,$$

where p denotes the true event rate of primary study endpoint in the target population. If the null hypothesis

(H₀) is rejected at the one-sided 0.025 statistical significance level, it is considered that the performance goal for the primary endpoint has been reached.

The analysis set of all enrolled subjects will be used for the analysis. The primary study endpoint is a dichotomous study outcome; hence, an exact method based on the binomial distribution will be used for the hypothesis testing.

Primary Endpoint Calculation:

A subject will be a failure on the primary endpoint if the subject either failed on access/deployment or had an MDE within 30 days. A subject will be a success on the primary endpoint if the subject is confirmed for access and deployment success as well as free from MDE. The failure rate of the primary endpoint is the percent of failures in all the evaluable subjects for the endpoint, i.e., in total number of failures and successes. Note that a subject who had an MDE within 30 days is one of the subjects in m as defined below. A subject who is free from MDE is one of the subjects in k as defined below.

MDE Rate Calculation:

All MDEs will be adjudicated by the Clinical Event Committee (CEC) per study protocol. MDE rate will be calculated as follows (Table 5):

Table 5: MDE Rate Calculation:

MDE rate = $m/(m + k)$	Within 30 Days	Within 183 Days	Within 365 Days
m = No. of Subjects Who Had MDE(s)	No. of subjects who had at least one MDE with onset day from Day 0 to Day 30, inclusive.	No. of subjects who had at least one MDE with onset day from Day 0 to Day 183, inclusive.	No. of subjects who had at least one MDE with onset day from Day 0 to Day 365, inclusive.
k = No. of Subjects Who Had No MDE	No. of subjects who have been in study for at least 1 day and without an MDE.	No. of subjects who have been in study for at least 91 days and without an MDE.	No. of subjects who have been in study for at least 305 days and without an MDE.

If a subject is early terminated from the study, the last day that the subject has been seen will be the duration in study, which can be the day of last follow-up, last imaging taken, an AE reported, or withdrawal from the study. If a subject is still in the study, the duration in study will be the time from index procedure to the cut off day that the database is locked or data snapshot is taken.

Subgroup analyses by-sex, by-race (based on subjects enrolled in the US only, since collection of race and ethnicity data may not be allowed outside the US as per local law and regulation), FreeFlo versus Closed Web configuration as proximal component, percutaneous access versus non-percutaneous, and by-region/study site will be performed on the primary study endpoint using descriptive statistics and reviewed for

clinical significant difference.

Secondary Endpoints

30-day Secondary Endpoint

The following secondary endpoints will be evaluated within 30 days post treatment:

- Peri-operative mortality
- All adverse events (AE) within 30 days including:
 - Major Adverse Event(s) (MAE)
 - Serious Adverse Event(s) (SAE)
- Secondary procedures
- Loss of stent graft patency at 30 day visit based on imaging findings
- Endoleaks at 30 day visit based on imaging findings

Detailed definitions of MAEs are defined in the Clinical Investigational Plan Appendix L.2.2. MAEs will be identified using codes in the Medical Dictionary for Regulatory Activities (MedDRA) provided by the Medtronic Clinical Safety group.

6-month Secondary Endpoints:

The following secondary endpoints will be evaluated:

- All-cause mortality within 183 days
- Aneurysm-Related Mortality within 183 days
- MDEs within 183 days
- All AEs within 183 days including:
 - MAEs
 - SAEs
- Secondary procedures within 183 days
- Loss of stent graft patency within 6 months based on imaging findings
- Endoleaks at 6 months based on imaging findings

- Stent graft migration at 6 months as compared to 1-month imaging
- Aneurysm expansion > 5mm at 6 months based on imaging findings relative to the 1-month visit

12-month Secondary Endpoints

The following secondary endpoints will be evaluated:

- All-cause mortality within 365 days
- Aneurysm-Related Mortality within 365 days
- MDEs within 365 days
- All AEs within 365 days including:
 - MAEs
 - SAEs
- Secondary procedures within 365 days
- Loss of stent graft patency within 12 months based on imaging findings
- Endoleaks at 12 months based on imaging findings
- Stent graft migration at 12 months as compared to 1-month imaging
- Aneurysm expansion > 5mm at 12 months based on imaging findings relative to the 1-month visit

Secondary endpoints are to be assessed beyond 12 months. The following secondary endpoints are to be evaluated at 24, 36, 48, and 60 months:

- All-cause mortality
- Aneurysm-Related Mortality
- MDEs
- All AEs and SAEs
- Secondary procedures
- Loss of stent graft patency based on site reported imaging findings
- Endoleaks based on site reported imaging findings

- Stent graft migration as compared to 1-month imaging
- Aneurysm expansion > 5mm based on site reported imaging findings relative to the 1-month visit

Health-related quality of life outcomes are to be assessed at all scheduled follow-up visits using the EQ-5D questionnaire.

Stent graft migration will be determined by the core lab or site imaging case report from (CRF). Core lab assessment and site reported result will be analyzed separately. Aneurysm expansion will be calculated. When 1-month image is not available, the latest image taken prior to 1-month will be used for calculation.

Descriptive statistical analyses will be performed on secondary endpoints. No inferential statistical analysis is planned for secondary endpoints.

Non-image endpoints event rates such as mortality, secondary procedures, MAEs, SAEs, conversion to open surgery, and thoracic aortic aneurysm ruptures through 1 year will be calculated in the same way as the MDE rate, specified in Table 5. The event rates beyond 1 year through 5 years will be analyzed using Kaplan Meier method.

Imaging based Event Rate Calculation:

Unless otherwise specified, imaging assessment will be performed by site as well as the core lab. Assessments from the core lab will be the primary result for the PMA and PMA-s submissions and analyzed separately from those by site. Imaging based event rate will be calculated using statistical analysis windows as follows (Table 6):

Table 6: Imaging based Event Rate Calculation:

Event rate = m/n	At 1 Month	At 6 Months	At 12 Months
m = No. of Subjects Who Had Event(s)	No. of subjects who had an event with scan day within the 1-month window.	No. of subjects who had an event with scan day within the 6-month window.	No. of subjects who had an event with scan day within the 12-month window.
n = No. of Subjects Who Had Readable Images	No. of subjects who had a readable image within the 1-month window.	No. of subjects who had a readable image within the 6-month window.	No. of subjects who had a readable image within the 12-month window.
Event rate = m/n	Through 1 Month	Through 6 Months	Through 12 Months
m = No. of Subjects Who Had Event(s)	No. of subjects who had an event with scan day within the 1-month window.	No. of subjects who had an event with scan day within 1- or 6-month windows.	No. of subjects who had an event with scan day within 1-, 6- or 12-month windows.
n = No. of Subjects Who Had Readable Images	No. of subjects who had a readable image within the 1-month window.	No. of subjects who had an event (counted in m) or had a readable image within the 6-month window.	No. of subjects who had an event (counted in m) or had a readable image within the 12-month window.

The imaging based event rates by visit at 24, 36, 48 and 60 months will be calculated in a similar way as above; i.e., m = number of subjects who had an event with scan day within the statistical analysis window of the specific time point; n = number of subjects who had a readable image within the 12-month window.

The cumulative event rate through 24, 36, 48 and 60 months will be estimated using survival analysis. Kaplan-Meier estimates, along with its standard error using the Greenwood method, will be reported for non-image based events. The image-based events are interval censored data and the interval censored survival analysis method will be used to calculate the event rates.

When reporting the site reported endoleaks, both site imaging findings and the events treated during secondary procedures will be accounted for in the analysis.

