7.2. General Methodology

In general, qualitative parameters will be described by their distribution frequencies; quantitative parameters will be described by their mean, standard deviation, minimum, maximum, median, and number of subjects with assessable data.

For events such as adverse events (AE), deaths and secondary procedures, that can occur or are observed at any time during the study, no time window will be applied. For such events, an event that occurs “within 1 month or 30 days” is an event that takes place between Days 0 to 30, inclusive. Similarly, an event that occurs “within 12 months or 365 days” is an event occurring between Day 0 to Day 365, inclusive. Date of event onset will be used to determine when the event occurred. Day 0 is referring to the day of index procedure.

For image-based assessments, such as stent-graft endoleak, patency, and other observations, the following time windows will be applied for by-visit data summaries:

Table 3: Time Windows for Statistical Analyses

Study Visit	Target Day	Time Window
Implant	Day 0	Day 0
1 Month	Day 30	1 – 90 days
6 Months	Day 183	91 – 304 days
12 Months	Day 365	305 – 548 days
24 Months	Day 730	549 – 913 days
36 Months	Day 1095	914 – 1278 days
48 Months	Day 1460	1279 – 1643 Days
60 Months	Day 1825	1644 – 2009 days

Unless otherwise specified, if different type of images are used and have different finding in the same time window, the imaging technique and sensitivity matrix (CIP Appendix L.3, also see Table 4 below) will be applied. Finding from higher visibility image will be used for analysis. If there are two or more assessments in the same time window, then the assessment closest to the target day will be used in the analysis of event rate at a given time point.

Table 4: Imaging Matrix

Anatomy/Stent Graft Issue Detected	CT with contrast	CT without contrast	MRI with contrast	MRI without contrast	Angiogram/, Aortogram, and Arteriogram
Diameter and Length	1	2	1	2	3
Stent graft migration	1	2	1	2	2-3
Stent graft fracture	2	3	2	3	2-3
Stent graft kinking	2	3	2	3	2-3
Collapse of stent graft	2	3	2	3	2-3
Stent graft twisting	2	3	2	3	2-3
Stent graft patency	1	4	1	4	2-3
Endoleaks	1	4	1	4	2-3
False lumen perfusion	1	4	1	4	2-3
Occlusion	1	4	1	4	2-3
Stenosis	1	4	1	4	2-3
Stent Graft Fabric Defect	1	4	1	4	2-3
1= Highly visible 2 = visible 3 = Not very visible (potential artifacts) 4 = Invisible					

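### The 30-day primary test counts a subject as MDE-free after one day in study, so event-free early leavers enter as successes

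*SAP*

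**What the plan says.** The rule is built up in SAP 7.9.

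- **Success** requires that "the subject is confirmed for access and deployment success as well as free from MDE".
- **MDE-free** is then tied to Table 5: "A subject who is free from MDE is one of the subjects in k as defined below".
- **The denominator** is failures plus successes; the rate is "the percent of failures in all the evaluable subjects for the endpoint, i.e., in total number of failures and successes".
- **Table 5, within 30 days**, defines k as "No. of subjects who have been in study for at least 1 day and without an MDE".
- **Table 5, within 183 and 365 days**, uses "No. of subjects who have been in study for at least 91 days and without an MDE" and "No. of subjects who have been in study for at least 305 days and without an MDE".
- **Duration in study** for leavers is set below the table: "If a subject is early terminated from the study, the last day that the subject has been seen will be the duration in study".

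Elsewhere in the SAP, section 5 times the primary analysis at 87 evaluable subjects reaching 30 days, and section 6 enrols 100 to secure those 87. Section 7.4 makes a tipping-point analysis for missing primary-endpoint data optional.

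**The concern.** Taken together, these statements score an implanted subject last seen on Day 2 without an event as a 30-day success. Nothing in either document requires an individual success to have been followed to about Day 30.

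The three thresholds (1, 91 and 305 days) are the lower bounds of the 1-, 6- and 12-month windows in SAP Table 3. SAP 7.2 sets those windows for image-based assessments. For events such as deaths and secondary procedures it says, of events "that can occur or are observed at any time during the study, no time window will be applied". The start of an imaging window says when a scan may count. It does not show that a subject was observed for events over the period. The mismatch is greatest in the column that matters most: the minimum is 1/30 = 3% of the period at 30 days, against 91/183 = 50% and 305/365 = 84% in the other two.

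At stake is the test against the 16% performance goal, the only hypothesis test at PMA submission. Table 5 classes these subjects as observed successes, not as missing, so the optional tipping-point analysis would not necessarily reach them. SAP 7.9 applies the same rule to the non-image secondary event rates through 1 year, but those are descriptive.

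**Working it through.** **Inputs from the SAP (sections 6 and 7.9).** Exact one-sided binomial test, null rate 16%, significance level 0.025, assumed true rate 6%, 87 evaluable subjects, stated power 85%, minimum enrolment 100.

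**Assumed, because the documents do not give them.** L is the number of event-free or partly observed subjects leaving before Day 30, taken from 0 to 13 (100 − 87). f is the share of a leaver's 30-day risk already seen at exit. Exit is taken as unrelated to outcome.

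**1. Reproduce the plan.** The goal is met when P(Bin(n, 0.16) ≤ x) ≤ 0.025.

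| n | Largest x that passes | Exact size | Power at 6% |
|---|---|---|---|
| 87 | 7 | 0.0233 | 0.849 |
| 94 | 7 | 0.0115 | 0.797 |
| 95 | 8 | 0.0239 | 0.883 |
| 100 | 8 | 0.0147 | 0.854 |

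The stated 85% at n = 87 is reproduced. The limit rises from 7 to 8 at n = 95.

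**2. Rule as written: 87 completers plus L leavers.** This is the case closest to the section 5 trigger.

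Type I error = P(Bin(87, 0.16) + Bin(L, 0.16f) ≤ limit for 87 + L)

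| L | n | Limit | f = 0 | f = 0.5 | f = 0.75 |
|---|---|---|---|---|---|
| 1 | 88 | 7 | 0.0233 | 0.0222 | 0.0217 |
| 5 | 92 | 7 | 0.0233 | 0.0183 | 0.0161 |
| 7 | 94 | 7 | 0.0233 | 0.0166 | 0.0139 |
| 8 | 95 | 8 | 0.0495 | 0.0349 | 0.0289 |
| 10 | 97 | 8 | 0.0495 | 0.0319 | 0.0252 |
| 11 | 98 | 8 | 0.0495 | 0.0305 | 0.0235 |
| 13 | 100 | 8 | 0.0495 | 0.0278 | 0.0204 |

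With 1 to 7 leavers there is no inflation. With half the risk seen, every L from 8 to 13 exceeds 0.025; with three quarters seen, only 8 to 10 do. The f = 0 column is a bound that would not be reached, because access failures, deployment failures and primary conversions are seen on Day 0.

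**3. Leavers inside a denominator of 87.** Type I error = P(Bin(87 − L, 0.16) + Bin(L, 0.16f) ≤ 7). At f = 0.5 it is 0.0258 for L = 2 and 0.0299 for L = 5. The definition of evaluable in 7.9 allows this reading; the section 5 wording on reaching 30 days speaks against it.

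**4. Effect on a result.**

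- 8/87: p = 0.0495, goal missed.
- Add 8 event-free early leavers, 8/95: p = 0.0239, goal met.
- One unseen failure among those 8, 9/95: p = 0.0487, goal missed.

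**5. Direction of bias at a true 16%, f = 0.5.** Expected rate as written = (87 × 0.16 + L × 0.08)/(87 + L):

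- L = 8: 14.56/95 = 15.3%
- L = 13: 14.96/100 = 15.0%

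**The case against.** The strongest reply is that the effect is nil in the most plausible range. With up to 7 leavers beyond 87 completers, the rule as written and a stricter rule give the same test decision, and 8 event-free leavers with unknown status in 30 days would be many. VALOR II hints at fewer: its 30-day figure is 9/160 (protocol C.7) and its 1-year figure 11/153 (SAP 6), so at most 7 of 160 were lost to the denominator over a year. That evidence is inconclusive. The evaluability rule behind 160 and 153 is not stated, the 160 could itself come from a one-day rule, and the SAP's own allowance of 13 points the other way.

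Event timing also matters. If 90% of the risk is seen before exit, only L = 8 exceeds 0.025 (0.0258). The worked example sits at the step in the rejection limit: 8/94 gives p = 0.0262 and misses. These points limit the size but leave the direction of the bias unchanged.

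Sections 5 and 6 tie evaluability to 30 days, but 7.9 defines evaluable as failures plus successes, which leads back to the one-day rule. It is fair to say that the no-window sentence in 7.2 concerns which events count, not how long a subject must be followed. The argument needs only that the Table 3 windows were set for imaging.

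Finally, SAP 3 names the US protocol as the primary resource for clarification. It was not available and may be stricter. Table 5 would then still need to match it, because analysts will program from the table.

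**Conclusion.** The concern holds. As written, the plan scores an event-free early leaver with a confirmed implant as a 30-day success in the only PMA hypothesis test, and this can only understate the failure rate compared with full follow-up of the same subjects. With 87 completers, type I error is not inflated by 1 to 7 leavers. It is 0.035 or 0.029 with 8, and 0.028 or 0.020 with 13 (half or three quarters of the risk seen). These figures rest on an assumed number of leavers, assumed event timing and exit unrelated to outcome. It should be fixed before analysis; confidence is medium, mainly because the US protocol could not be consulted.

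**What to change.** Redefine k for 30 days as subjects with no MDE and either (a) MDE status confirmed through about Day 30, or (b) death before Day 30 adjudicated as not an MDE. Treat other event-free leavers as non-evaluable. Whenever there are any, report a sensitivity analysis, either tipping point or all counted as failures. If the US protocol already defines evaluability at 30 days this way, align Table 5 with it.

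The cost is SAP wording and a status check or record look-up for subjects last seen before about Day 30. The fix has a small conservative bias, because leavers with events stay in m while event-free leavers drop out. At a true 16% and half the risk seen, the expected rate is 16.6% with 8 leavers and 17.0% with 13. Type I error stays at or below 0.0233.

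Power at a true 6%, with 87 completers and half the risk seen:

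| Leavers | Fix | As written |
|---|---|---|
| 0 | 0.849 | 0.849 |
| 5 | 0.831 | 0.831 |
| 8 | 0.820 | 0.904 |
| 13 | 0.801 | 0.891 |

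The stricter definition makes it important that the analysis waits for 87 subjects: with 85 or 86 evaluable the limit falls to 6 and power to 0.752 or 0.742.
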